**Testing a Training Program That uses Virtual Reality Technology to Improve Children's
Pedestrian Behaviors: A Randomized Controlled Trial**

#NCT-03960047

Sept 1 2019

TITLE

Testing a Training Program That uses Virtual Reality Technology to Improve Children's Pedestrian Behaviors: A Randomized Controlled Trial

NCT-03960047

SETTING

We focus on midblock crossing on two-lane bidirectional roads, without nearby traffic signals or crosswalks.

For SS-T sessions, a road has been identified (50 km limit) that provides opportunity for training in *where* and *how* to cross in the same types of road situations to be presented in VR-T. Traffic volume was recently measured for 7 days and varied from light (8 cars/min) to heavy (16 cars/min).^{13,30} This range for traffic volume will occur in VR-T.

For VR-T sessions, these occur in the VR lab at UG campus.

For pre and post measures, for all groups these occur in two settings: **(a)** street side (designated as "Field" below) with naturally varying traffic (children indicate where and how they will cross but do not do so), **(b)** in the VR lab in which children cross the virtual street in traffic using a gaming controller.

Note that the pre/post Field measures will be taken at two locations along the *same* road (randomized order, with one used for pre and the other for post), which controls for familiarity and minimizes risk of large variation in traffic volume between pre/post measures. The road is nearby the VR lab, which allows children to complete pre-test VR *and* Field measures during the *same* visit to UG; the same will occur for post-test measures. Posted speed is 50 km, which means traffic conditions to be tested on are ones that pose risk of severe injury at these ages.^{13,57}

TESTING PROTOCOL

Pre/Post measures for Where and How to Cross

[Note that pre- and post- measures are the same, and all children, regardless of group, complete all measures.]

Field Measures. For *where* to cross measures, the child selects the safest location to cross in 3 different street side situations (parked cars, hill, blind curve). For *how* to cross measures: the child stands 1 foot from the curb, with a pressure sensitive step plate in front of him (it connects to a laptop; a clear plastic wall prevents entry into the street), and completes a '2 step procedure' (based on observed traffic, take 2 steps forward, corresponding to initiating a street crossing;^{23,58} from this we estimate crossing measures. [NOTE: Street side testing is video recorded so traffic and crossing measures can be computed later; the PI has used this procedure before.⁵⁹]

VR Measures. The same measures as for Field, except completed within a virtual street environment.

Pre-Training Activities & Measures

VR-T. An initial Orientation and Movement-Control Training Module ensures all children are practiced with using the controller to navigate in the 3-D world to the same motor skill level, *before* starting pedestrian training. The controller allows them to vary their path, direction, and speed of walking and crossing.

SS-T. Children's average walking speed for crossing is determined⁵⁸ and then, in combination with video taken street side, is used to estimate crossing measures – so they do not cross in traffic, but only give initiation judgements. This is a common approach that the PI has used before.⁵⁹

Training Programs [All program decisions were informed by pilot testing.]

Each includes 6 training sessions of 30 minutes (2% of our pilot sample needed a break) and addresses *where* and *how* to look and cross. Performance is tracked on a trial-by-trial basis, and errors result in repetition of teaching trials, resulting in more training on skills they lack than those they have. Difficulty level generally increases over sessions as children acquire skills.

VR-T. Children experience trials from each of three training modules that are organized logically for how one crosses: **(1)** deciding *where to cross* (component skills: identify a safe place with parked cars, traffic on hills, traffic on blind curves); **(2)** *effective looking* (component skills: left-right-left, always left as one enters the road); **(3)** *how to cross safely* (component skills: check traffic in both directions, select larger gaps, start right in when car back bumper passes). On each trial, the computer talks and provides immediate feedback on performance so children know if they safely completed the trial (e.g., “Great job”) or what they did that was unsafe and why (replays of what the child did are shown and explained), and what to do instead. A component skill is tested (with explanatory feedback given for failures) until the child achieves at least 80% success over a minimum of 5 trials or completes 15 trials. They then move on to test another component skill, with failed component skills retested in a future session. Over sessions, they get repeated training on all modules and component skills, but repetition focuses mostly on skills they still need to achieve.

SS-T. This program is grounded in behavior theory (modeling, reinforcement) and modeled after Kerbcraft⁶⁰ a program shown to improve children’s safe crossing behaviors. The program also includes *where* and *how* content and is organized similarly to VR-T (modules, teach component skills, immediate feedback). Over sessions, they get training on all modules and component skills, with repetition focusing on weaker skills.

STATISTICAL ANALYSIS PLAN

The CONSORT flowchart diagram will guide all reporting of results and an intention-to-treat analysis will be conducted, as appropriate.

Covariates

Summary statistics will be computed for baseline and demographic characteristics. When imbalances occur between groups, despite randomization, these variables will be included as covariates. Likely covariates include: (a) Child age; (b) Child Pedestrian Experience questionnaire data (parent report), which yields average weekly distance walked and other potential covariate indices;⁶⁸ (c) # of days between pre- and post- tests; (d) family income.

Primary Analyses

Behaviors. We will document the baseline characteristics of each of the 3 groups (age, sex, walking experience, days between pre- and post- tests, family income, and traffic volume for field measures). We will produce point estimates and confidence intervals for the mean difference between pre- and post-immediate scores (i.e., change scores) for each group and each *where* (1 score), *how* (3 scores), and *consequence* (2 scores) outcome. We will then use linear regression of change score on group adjusting for covariates. We will extend this approach to multivariate (modeling multiple outcomes) linear regression incorporating all of the outcomes into one model and employing an adjustment for multiple comparisons. We will include interaction terms between group and sex to determine if child sex modifies program effects. An intention-to-treat approach will be followed. The goal is to assess for immediate gains following program completion in our outcomes (for Sustainability see Secondary Analyses).

Secondary Analyses

Behaviors. These will examine pre- to post-immediate changes in *Component Skills* performance (e.g., *where*: selecting safe location with parked cars) and examine from post-immediate to post-2 months later (to assess for sustainability of effects), comparing pre to post scores using the same approach as above.

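### The randomised order of the two Field locations is missing from the change-score model; pre-specifying it could narrow Field intervals, though a gain is not certain

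*Combined protocol and SAP*

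**What the plan says.** The Setting section places the pre and post Field measures at two points along the same road, in "randomized order, with one used for pre and the other for post". It says this controls for familiarity and "minimizes risk of large variation in traffic volume between pre/post measures".

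Under Testing Protocol, Field Measures, the child "selects the safest location to cross in 3 different street side situations (parked cars, hill, blind curve") for the where-to-cross score. The how-to-cross measures come from a stepping procedure in live traffic.

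Under Statistical Analysis Plan, Covariates, the rule is: "When imbalances occur between groups, despite randomization, these variables will be included as covariates". The likely covariates named are age, pedestrian experience, days between tests and family income. Location order is not among them.

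Under Primary Analyses, the model is "linear regression of change score on group adjusting for covariates", then extended to a multivariate regression "incorporating all of the outcomes into one model". Six scores are listed (one where, three how, two consequence), without saying whether each is Field, VR or a combination. Secondary Analyses adds a comparison from post-immediate to 2 months.

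**The concern.** Half the children (if order is allocated 1:1) go from location A to location B and the rest from B to A. If one location is harder, the first half's Field change shifts by the difference in one direction and the second half's by the same amount in the other. With no order term, that spread goes into the residual variance.

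The covariate rule does not address this, because balance and precision are separate matters. A location difference stays in the residual even when order is evenly split across groups, and an even split is exactly when an imbalance trigger leaves order out. In that case the reported standard error is too large for the actual sampling variation, and the test is conservative.

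What is at stake is the width of Field intervals and some power. The validity of the comparison is not in question.

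**Working it through.** **Inputs.** From the documents: two locations in randomised order, three groups, a change-score regression without order. Not in the documents, and assumed here: location difference δ of 0.1, 0.25 or 0.5 (in SDs of a single-occasion score); pre/post correlation r of 0.3 to 0.7; n per arm of 20, 30 or 60; equal arms; order randomised per child, 1:1; two-sided alpha of 0.05. The plan gives no power or precision figure to reproduce.

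**Step 1: variance with order left out.** With unit SD at each test, the change has variance 2(1−r). Order adds +δ or −δ, which contributes δ². The inflation is f = 1 + δ²/(2(1−r)), and the interval is √f times as wide.

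**Step 2: power, order not balanced within arms.** Set the effect to give 80% power with order modelled (1.96 + 0.84 = 2.80 standard errors). Without the term, power = Φ(2.80/√f − 1.96).

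**Step 3: type I error, order exactly balanced within arms.** The true standard error excludes δ but the reported one includes it, so type I error = 2(1 − Φ(1.96√f)).

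Results at r = 0.5, where 2(1−r) = 1:

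| δ | f | Width √f | Power without order (step 2) | Type I error (step 3) |
|---|---|---|---|---|
| 0.1 | 1.010 | 1.005 | 0.796 | 0.049 |
| 0.25 | 1.063 | 1.031 | about 0.78 | 0.043 |
| 0.5 | 1.250 | 1.118 | 0.707 | 0.028 |

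Example: Φ(2.80/1.118 − 1.96) = Φ(0.544) = 0.707. Across r = 0.3 to 0.7 the width factors are 1.004–1.008, 1.02–1.05 and 1.09–1.19.

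**Step 4: simulation.** Three arms, 60 per arm, r = 0.5, 20,000 runs per setting.
- Order permuted across arms: the mean null contrast was within 0.004 of zero, so there is no bias. Type I error without order was 0.049–0.053. Power without/with order was 0.791/0.792, 0.770/0.792 and 0.700/0.794.
- Order exactly balanced: type I error without/with order was 0.046/0.047, 0.045/0.051 and 0.029/0.049.

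**Step 5: cost of the term.** It uses one residual degree of freedom. If order is not balanced within arms, chance imbalance also inflates the contrast variance by about 1/(3(n−1)):
- n = 20: 1/57 = 0.0175, SE × 1.009
- n = 30: 1/87 = 0.0115, SE × 1.006
- n = 60: 1/177 = 0.0056, SE × 1.003

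**Step 6: break-even.** Setting δ²/(2(1−r)) = 1/(3(n−1)) at r = 0.5 gives δ = √(1/57) = 0.13, √(1/87) = 0.11 and √(1/177) = 0.075 at 20, 30 and 60 per arm. Below these values the term costs slightly more than it saves.

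**Step 7: a score averaging Field and VR.** With correlation ρ between the two changes, f = 1 + δ²/(4(1−r)(1+ρ)). At r = 0.5 and ρ from 0.5 down to 0, width is 1.002–1.003, 1.010–1.016 and 1.04–1.06, so the effect is roughly halved or less.

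**The case against.** The strongest reply is that nothing in the plan is wrong. Randomising the order is itself the design control, and the regression without an order term is unbiased. With order permuted across arms it also holds its nominal error rate. A reader might infer that ignoring location distorts the group comparison; the design and the simulation both say otherwise. The covariates are introduced only as likely ones, so order is not excluded. All of this stands.

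Second, the only evidence on size points to a small difference. Both locations are on one road, chosen to limit variation in traffic volume. The Testing Protocol also says that pre and post measures are the same, which suggests that all three where-to-cross situations appear at both tests. That weakens the argument from fixed site features without settling it: presenting the same types of situation does not establish equal difficulty. No passage supports a difference as large as 0.5 SD.

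Third, a reader might take the term as a guaranteed and nearly free gain. It is not, given the break-even values above: at 20 per arm and 0.1 SD, with order not balanced within arms, adjustment is slightly worse.

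Fourth, the conservative type I error needs order balanced within arms, and per-child randomisation is an inference from a short phrase; neither is documented. Nor do the documents show that adding "traffic volume for field measures" as a standing covariate would help, so this point makes no such recommendation.

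**Conclusion.** The point holds as an optional refinement. The change-score model leaves out a factor that the design randomises, and the imbalance rule would not reliably bring it in. The consequence is possible loss of precision in the pre to post-immediate Field results, without bias.

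At r = 0.5 the loss is about 0.5%, 3% or 12% in interval width for assumed location differences of 0.1, 0.25 or 0.5 SD, before the cost of the term. The likely range is towards the lower end, given the same-road choice, and the net gain may be nil or slightly negative if the locations are very alike and the arms small. The location difference, correlation, sample size and per-child randomisation of order are all assumptions.

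The conclusion does not extend to scores based on VR alone, which have no Field location, nor directly to the 2-month comparison. The Setting section assigns locations only to pre and post, so A-then-B order does not define the location at 2 months.

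**What to change.** Confirm that order is randomised per child and recorded. Then add a sentence to Primary Analyses: location order (A then B, or B then A) enters as a fixed factor in the pre to post-immediate change models for every score that is Field or includes Field data, regardless of observed balance. The SAP should identify which of the six scores these are.

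For the post-immediate to 2-month analysis, state which location is used at 2 months and define a separate location term.

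The cost is the added SAP text, one degree of freedom per outcome and, if order is not balanced within arms, a standard error about 1.009 times as large at 20 per arm or 1.003 times at 60. No new data or visits are needed if order is already recorded.

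### Field *how* and *consequence* change scores carry traffic variation that testing on one road does not limit; adjust for traffic at both tests in every such model, whatever the group balance

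*Combined protocol and SAP*

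**What the plan says.** Under SETTING, the Field tests take place at the street side "with naturally varying traffic (children indicate where and how they will cross but do not do so". Two locations on one road are used: "randomized order, with one used for pre and the other for post), which controls for familiarity". The same sentence adds that this "minimizes risk of large variation in traffic volume between pre/post measures".

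The only traffic count is given for the training road. The text begins "For SS-T sessions, a road has been identified (50 km limit" and continues "Traffic volume was recently measured for 7 days and varied from light (8 cars/min) to heavy (16 cars/min"). The Field test road has the same posted speed and lies near the VR lab. The document does not say whether it is the same road.

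Under TESTING PROTOCOL, Field Measures, the *how* task is a two-step start made in response to the traffic the child sees. Crossing measures are then estimated from it. The plan notes that "Street side testing is video recorded so traffic and crossing measures can be computed later". On the VR tests it says "The same measures as for Field, except completed within a virtual street environment".

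In the Statistical Analysis Plan, Covariates, variables enter the model when the groups are imbalanced on them. The likely ones named are age, pedestrian experience, days between tests and family income. Under Primary Analyses, Behaviors, the characteristics to be documented by group include "days between pre- and post- tests, family income, and traffic volume for field measures". The analysis then gives a mean change with interval within each group, followed by a regression of change score on group.

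**The concern.** The stated safeguard and the source of variation do not match. Keeping to one road removes road-to-road differences. The plan's own count shows a range of 8 to 16 cars/min on a single road across a week, which is variation over time. Nothing in the document ties a child's tests to the same time of day, type of day or volume.

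The gaps on offer depend on traffic, and the Field *how* scores come from the gap at which the child starts. The document does not define the two *consequence* scores. If they are estimated from the same start and video, as seems likely, they inherit this dependence. *Where* to cross is a choice of location and is less directly affected.

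The covariate rule is not aimed at this problem. It is triggered by a difference between groups, whereas the noise comes from each child's own traffic change. Groups can be balanced on average traffic while individual changes still inflate the residual variance. At stake are the precision of the Field comparisons and the meaning of the within-group Field changes.

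**Working it through.** The documents give no sample size, power, alpha, SD or effect size, so there is no planned figure to reproduce. What follows is illustration on stated assumptions.

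**Inputs.** From SETTING: 8 and 16 cars/min, a ratio of 16/8 = 2.0 at the extremes. Assumed: this range applies to the Field road; arrivals are random (Poisson); a crossing takes 5 to 7 s; a child's pre and post volumes are independent and uniform on 8–16.

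**1. How far gaps depend on volume.** Mean headway is 60/8 = 7.5 s against 60/16 = 3.75 s. The chance that a random moment is followed by T clear seconds is exp(−vT/60).

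| T | 8 cars/min | 16 cars/min |
|---|---|---|
| 5 s | 51% | 26% |
| 6 s | exp(−0.8) = 45% | exp(−1.6) = 20% |
| 7 s | 39% | 16% |

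This describes the supply of gaps. It is not a child's score, because the child chooses when to step.

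**2. How large a child's traffic change would be.** A shift of at least 2 cars/min has probability (6/8)² = 56%, and of at least 4, (4/8)² = 25%. By simulation, the median ratio of the higher to the lower volume is 1.22; 17% of children exceed 1.5-fold and 0.5% exceed 1.9-fold.

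**3. Share of change-score variance.** The variance of the pre-to-post difference in log volume is 0.078. For a log-scale gap score with elasticity e to volume and residual change SD s, the share is R² = 0.078e²/(0.078e² + s²). The values of e and s are assumed.

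| e | R², s = 0.5 | R², s = 0.3 |
|---|---|---|
| 0.25 | 2% | 5% |
| 0.5 | 7% | 18% |
| 1 | 24% | 47% |

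**4. Cost to the group comparison.** Leaving traffic out inflates the sample size needed by 1/(1 − R²). Power that would be 80% without traffic noise becomes approximately Φ(2.80·√(1 − R²) − 1.96), assuming a two-sided 5% test.

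| R² | N inflation | Power |
|---|---|---|
| 5% | 1.05 | 78% |
| 10% | 1.11 | 76% |
| 25% | 1.33 | 68% |
| 50% | 2.0 | 51% |

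**5. Bias or noise?** In a simulation of two arms of 40 (assumed) with no treatment effect, change = noise (SD 1) + β × (post minus pre cars/min), and traffic was independent of arm. Each setting had 20,000 runs.

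- Between groups, the mean difference was about 0 and type I error was 4.8% to 5.1%, even when every post-test averaged 2 cars/min higher.
- Within a group, with no shift in average traffic, false change appeared in about 5% of runs. With post-tests 2 cars/min higher, it appeared in 21% (β = 0.1) and 75% (β = 0.3).

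The variance of the traffic difference is 2 × 8²/12 = 10.67. These slopes therefore correspond to traffic shares of 0.107/1.107 = 10% and 0.96/1.96 = 49%.

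**The case against.** The strongest reply is that the trial compares randomised groups. Traffic that varies independently of group cancels on average, and step 5 confirms this: no bias, and type I error at its nominal level. That stands. A reader might infer that the Field treatment effects are biased. This would need one group's tests to fall in systematically different traffic, and the documents show no such scheduling.

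A reader might also infer that children typically face a twofold traffic difference between tests. Twofold is the limit of a range given only for the training road. The documents do not say which hours were counted or whether Field tests span them. Even under the wide assumption in step 2, the median ratio is 1.22.

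The effect on scores is not established either. Children respond to the traffic they see, no time limit for stepping is stated, and the scoring rules are not given. At the low end of step 3 the share is 2%, which is trivial.

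The plan does not ignore traffic. It records it on video, lists it among the characteristics to document and can adjust for it under the imbalance rule. The list of likely covariates is not exhaustive. The documented list also includes days between tests, so it is not confined to pre-test variables, and traffic volume may be meant at both tests. The wording does not settle this. The plan claims only to reduce the risk of large variation, and uses the language of control for familiarity alone.

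Finally, the same measures are taken in VR, so conclusions do not rest on the Field scores alone. That is true, but the VR scores do not correct the Field scores, which are separate outcomes in a separate setting.

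None of this answers two points: one road does not limit variation over time, and adjustment triggered by group imbalance does not target each child's traffic change.

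**Conclusion.** The point holds as a cheap gain in precision and a caution on interpretation. It is not a threat to the validity of the randomised comparison. Traffic noise in the Field *how* and *consequence* scores is avoidable with data the trial already records, and the current covariate rule may leave it in.

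The loss could be negligible (2% of variance, N inflation 1/0.98 = 1.02) or substantial (47%, 1/0.53 = 1.89). The documents do not narrow this range. It rests on the assumed elasticity and residual SD, on independent uniform volumes, and on carrying the training-road range over to the Field road.

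The within-group Field estimates are the weaker part of the analysis. If average traffic differs between pre- and post-tests, they can show change without any change in skill, and randomisation offers them no protection.

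**What to change.** 1. Compute cars/min from the existing video at every Field test, over a fixed window that does not depend on when the child steps, such as a set interval before the first trial. This condition matters. If counting stops when the child steps, a trained child who waits for a larger gap alters the count, and the covariate could absorb part of the treatment effect.
2. Pre-specify pre and post volume, or their difference, as a term in every Field *how* and *consequence* model, regardless of group balance. If Field tests are repeated at 2 months, use the volumes at the two tests being compared.
3. State that within-group Field change will not be read as skill gain alone, and report mean traffic at each test by group alongside it.
4. Where feasible, offer the same time-of-day slots to all groups and match each child's post-test slot to the pre-test slot. This also closes the scheduling route to bias.

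The cost is one or two degrees of freedom per model and minor scoring of video already taken. Matching slots makes appointments less flexible. The documents give no staffing or scheduling details from which to judge how much, so item 4 is conditional and items 1 to 3 do not depend on it.

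### The primary regression takes its covariates from observed group imbalance, with no criterion and an open list, and one candidate, days between tests, is called baseline although it is known only at post-test.

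*Combined protocol and SAP*

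**What the plan says.** The Covariates section says that baseline and demographic characteristics will be summarised, and then gives its only inclusion rule: "When imbalances occur between groups, despite randomization, these variables will be included as covariates". It names no test, threshold or standardised difference. The candidates are introduced as likely ones, so the list is not closed. One candidate, the parent questionnaire, is itself open, being described as a source "which yields average weekly distance walked and other potential covariate indices". The list ends "c) # of days between pre- and post- tests; (d) family income".

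Primary Analyses (Behaviors) then says: "We will then use linear regression of change score on group adjusting for covariates". That sentence names no covariates and carries no condition. The opening sentence of the same paragraph lists the baseline characteristics to be documented for the three groups, and includes "days between pre- and post- tests, family income, and traffic volume for field measures" among them. On sex it adds: "We will include interaction terms between group and sex to determine if child sex modifies program effects". All outcomes are later combined in one model "employing an adjustment for multiple comparisons", of a kind not stated.

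**The concern.** There are two issues, of unequal weight.

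**The covariate rule.** Two analysts could follow this plan, fit different primary models, and both say they complied. The rule also selects on the wrong property. Under randomisation, an observed baseline imbalance is chance. What makes adjustment worthwhile is that a variable predicts the change score, and imbalance carries no information about that. The rule can therefore leave out a prognostic variable that has already been collected. At stake are a determinate primary analysis and some precision.

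**Days between tests.** A variable fixed only when the post-test takes place cannot be a baseline characteristic. As a candidate covariate it allows the primary group comparison to be conditioned on something that happens after assignment and training.

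**Working it through.** The documents give no sample size, effect size, significance level or correlation, so there is no figure of the plan's own to reproduce. They do give three groups and six outcome scores (1 *where*, 3 *how*, 2 *consequence*). Everything else below is assumed: 50 children per group unless stated, a true difference of 0.5 SD for one pairwise contrast, and a two-sided 5% test.

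**1. The text side by side.** The Covariates section brings variables in when groups are imbalanced, which naturally reads as only then. Primary Analyses adjusts without condition. Neither section supplies a criterion or a final list. Four candidates taken as single variables already allow 2^4 = 16 covariate sets, before any further questionnaire indices.

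**2. How far the missing criterion decides the model.** This is the probability that one covariate enters by chance under perfect randomisation. For a trigger on the largest pairwise standardised difference exceeding c, it is approximately the probability that the studentised range of three means (3n − 3 df) exceeds c√n. At n = 50, 0.25 × √50 = 1.77 and 0.1 × √50 = 0.71.

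| Trigger | n = 30 | n = 50 | n = 80 |
|---|---|---|---|
| ANOVA p < 0.05 | 5% | 5% | 5% |
| largest difference > 0.25 SD | 60% | 43% | 26% |
| largest difference > 0.1 SD | 92% | 87% | 80% |

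All three are plausible readings of imbalance. With four independent candidates and the p < 0.05 trigger, the chance that at least one enters is 1 − 0.95^4 = 18.5%.

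**3. Precision lost with a trigger fixed in advance.** Simulation with one covariate, 20,000 trials per cell, sex and group-by-sex terms in the model; r is the correlation with the change score.

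| r | Always adjust | p < 0.05 | > 0.25 SD | > 0.1 SD | Loss (points) |
|---|---|---|---|---|---|
| 0.1 | 69.0% | 68.8% | 68.7% | 68.9% | 0.1 to 0.3 |
| 0.2 | 70.3% | 68.6% | 69.2% | 70.0% | 0.3 to 1.7 |
| 0.3 | 73.2% | 69.5% | 71.3% | 72.8% | 0.4 to 3.7 |

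With Bonferroni over six scores standing in for the unspecified multiplicity adjustment, r = 0.3 gives 46.8% against 42.7%, 44.2% and 46.2%, a loss of 0.6 to 4.1 points. The multivariate model itself was not simulated.

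**4. Type I error.** With a trigger fixed in advance it ran from 3.4% to 5.2%, so at or below nominal within simulation error. As an outer bound only, taking the smallest p over all 16 sets of four independent covariates gave 6.4%, 7.6%, 10.0% and 13.7% at r = 0, 0.1, 0.2 and 0.3 each.

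**5. Days between tests.** The interval ends at the post-test, after training. If assignment does not shift it, the model with days targets the same group contrast without bias. If assignment does shift it, and the interval shares causes with the outcome, adjusting could bias the contrast. Both described programs have six sessions, but neither calendar spacing nor the third group's schedule is given. The documents therefore neither state nor exclude a shift, and they supply no input for a bias figure. A real shift by group would also be the sort of imbalance that brings days into the model.

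**6. Cost of always adjusting.** Without covariates, the noncentrality is 0.5/√(2/50) = 2.50 on 147 df, giving power of 70.0%. With k useless covariates the variance rises by the factor 1 + k/(3n − 3 − k − 1). For k = 4 this is 1 + 4/142 = 1.028, so the noncentrality is 2.50/√1.028 = 2.47 on 143 df and power is 68.8%, a loss of 1.2 points. At 3 × 30 power falls from 48.2% to 46.4%, and at 3 × 80 from 88.3% to 87.7%. Sex and group-by-sex terms lower the starting power at 3 × 50 by about one point (roughly 69.0% to 67.9% with the four covariates), but the loss from the covariates hardly changes. Four covariates break even if together they explain about 2.8% of change-score variance at 3 × 50.

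**The case against.** Adjusting for imbalanced variables is common practice, and a mechanical trigger is not anti-conservative. That stands: step 4 shows no inflation, and step 3 shows negligible loss for weak covariates. But common practice supplies neither the missing criterion nor a closed list.

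Primary Analyses can be read as unconditional adjustment. That is possible, but it then names no covariates, so the model is still not determined.

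A reader might go further and infer that the rule inflates false positives to the 6% to 14% of the outer bound. The documents do not support that. The bound requires choosing the covariate set by its p-value, and nothing in them suggests this is intended.

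A reader might also infer that adjusting for days biases the group comparison. Nor is that shown: it needs assignment to shift the interval, and the documents are silent. What is established is that the label is wrong.

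Traffic volume is weaker still. Field testing happens at both times ("pre- and post- measures are the same, and all children, regardless of group, complete all measures"), so post-test traffic, if that is meant, is not baseline. But it is absent from the likely covariates, and the design limits its variation by using two locations on one road in randomised order. This is a labelling point only.

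**Conclusion.** The concern holds as a gap in pre-specification, and it should be fixed before group data are examined. The primary model is chosen after the fact, by an undefined rule, on a property unrelated to prognostic value. If the trigger were fixed, the consequence would be lost precision only: negligible for weak covariates, and up to about 4 power points for one covariate at r = 0.3. With it undefined, type I error control rests on analyst restraint and not on the plan. These sizes depend on the assumed 3 × 50 children, 0.5 SD effect and correlations, none of which comes from the documents. The open rule and the mislabelling of days can be read directly from the text and need no assumption. Removing days from the primary model is a precaution.

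**What to change.** Replace the imbalance rule with: *Every primary model includes the following covariates, whatever the observed balance*, followed by a closed list of variables measured at or before the pre-test. An example is the pre-test score of the outcome, child age, average weekly distance walked, family income and sex. The pre-test score is not on the plan's list. It is already collected and is a natural candidate because it is a component of the change score, but the sponsor may choose otherwise; what matters is that the list is fixed before the data are seen. Name sex explicitly, because Primary Analyses does not say whether the group-by-sex terms belong to the primary contrast model or to a separate step, and sex is not among the likely covariates. State that the parent questionnaire and income are collected at or before the pre-test, since the documents do not say when.

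Take days between tests, and any post-test traffic volume, off the baseline list. Report days by group and adjust for it only in a labelled sensitivity analysis.

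The cost is SAP wording, a few degrees of freedom and the loss of freedom to adapt the list later. No new data are needed. In power, four useless covariates cost the 1.2 points shown above. If sex entered as a fifth and were also useless, the factor would be 1 + 5/141 = 1.035 and the total loss at 3 × 50 about 1.5 points.
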